### 5.2 DEATHS

All deaths on study must be reported to IRBs overseeing the study, Study Monitor, FDA and Amryt (**or designee**) within 24 hours of notification of the death. In addition, all deaths within 30 days of last investigational drug dose and/or deaths occurring out to the last formal follow-up observational period, whichever is longer. For all deaths, autopsy reports (if applicable) and relevant medical reports must be sent to Amryt (**or designee**) along with the FDA, and relevant IRBs overseeing the study.

### 5.3 SERIOUS ADVERSE EVENT (SAE) DEFINITION

A serious AE (SAE) is any untoward medical occurrence that at any dose:

- results in death

- is life-threatening (defined as an event in which the subject was at risk of death at the time of the event; it does not refer to an event which hypothetically might have caused death if it were more severe)
- requires inpatient hospitalization or causes prolongation of existing hospitalization (see NOTE below)
- results in persistent or significant disability/incapacity
- is a congenital anomaly/birth defect
- is an important medical event (defined as a medical event(s) that may not be immediately life-threatening or result in death or hospitalization but, based upon appropriate medical and scientific judgment, may jeopardize the subject or may require intervention [e.g., medical, surgical] to prevent one of the other serious outcomes listed in the definition above.) Examples of such events include, but are not limited to, intensive treatment in an emergency room or at home for allergic bronchospasm; blood dyscrasias or convulsions that do not result in hospitalization.) Potential drug induced liver injury (DILI) is also considered an important medical event. (See Section 1.6 for the definition of potential DILI.)

Suspected transmission of an infectious agent (e.g., any organism, virus or infectious particle, pathogenic or non-pathogenic) via the study drug is an SAE.

Although pregnancy, overdose, cancer, and potential drug induced liver injury (DILI) are not always serious by regulatory definition, these events must be handled as SAEs. (See Section 1.4 for reporting pregnancies.)

**NOTE:**

The following hospitalizations are not considered SAEs for this research study protocol:

- a visit to the emergency room or other hospital department < 24 hours, that does not result in admission (unless considered "important medical event" or event life threatening)
- elective surgery, planned prior to signing consent
- admissions as per protocol for a planned medical/surgical procedure
- routine health assessment requiring admission for baseline/trending of health status (e.g., routine colonoscopy)
- medical/surgical admission for purpose other than remedying ill health state and was planned prior to entry into the study. Appropriate documentation is required in these cases
- admission encountered for another life circumstance that carries no bearing on health status and requires no medical/surgical intervention (e.g., lack of housing, economic inadequacy, care-giver respite, family circumstances, administrative).

#### **5.4 SERIOUS ADVERSE EVENT (SAE) COLLECTION AND REPORTING**

Following the subject's written consent to participate in the study, all SAEs, whether related or not related to study drug, must be collected, including those thought to be associated with protocol-specified procedures. All SAEs must be collected that occur during the screening period and within 30 days of discontinuation of dosing. If applicable, SAEs must be collected that relate to any later protocol-specified procedure (e.g., a follow-up skin biopsy).

The investigator should report any SAE occurring after these time periods that is believed to be related to study drug or protocol-specified procedure.

An SAE report should be completed for any event where doubt exists regarding its status of seriousness.

If the investigator believes that an SAE is not related to the study drug, but is potentially related to the conditions of the study (such as withdrawal of previous therapy, or a complication of a study procedure), the relationship should be specified in the narrative section of the SAE Report Form.

SAEs, whether related or not related to study drug, and pregnancies must be reported to Amryt (or designee) within 24 hours. SAEs must be recorded on the SAE Report Form or other appropriate forms approved by the responsible regulatory authority (e.g., the applicable MedWatch 3500 or CIOMS form); pregnancies on a Pregnancy Surveillance Form (electronic or paper forms). When using paper forms, the reports are to be transmitted via email or confirmed facsimile (fax) transmission to:

SAE Email Address: [contact]

SAE [contact]

For studies capturing SAEs/pregnancies through electronic data capture (EDC), electronic submission is the required method for reporting. The paper forms should be used and submitted immediately, only in the event the electronic system is unavailable for transmission. When paper forms are used, the original paper forms are to remain on site.

If only limited information is initially available, follow-up reports are required. (Note: Follow-up SAE reports should include the same investigator term(s) initially reported.)

If an ongoing SAE changes in its intensity or relationship to study drug or if new information becomes available, a follow-up SAE report should be sent within 24 hours to Amryt (or designee) using the same procedure used for transmitting the initial SAE report.

All SAEs should be followed to resolution or stabilization.

The term “severe” is often used to describe the intensity (severity) of a specific event (as in mild, moderate, or severe pain); the event itself, however, may be of relatively minor medical significance (such as severe headache). By contrast, the term “serious” is used to describe an event based on an event outcome or actions usually associated with events that pose a threat to a patient’s life or functioning. Seriousness (not severity) serves as a guide for defining regulatory reporting obligations.

If an SAE occurs, the investigator should initiate appropriate support procedures. Important medical events that may not be immediately life-threatening or result in death or hospitalization but that may jeopardize the subject or require intervention to prevent one of the outcomes listed above or result in urgent investigation may be considered serious. Examples include allergic bronchospasm, convulsions, and blood dyscrasias. If the adverse event is sufficiently severe in the investigator’s judgment, the subject should be removed from study and a termination assessment performed. The subject should be given appropriate care under medical supervision until symptoms cease.

Unexpected, related SAEs must be reported to the FDA in an expedited manner. (Refer to 21 CFR 312 and ICH E2A for guidance.) The investigator will determine expectedness by referring to the most current version of the Investigator’s Brochure. Adverse events that are deemed serious by the investigator (irrespective of suspected causation) should be reported according to local IRB guidelines. Unexpected and related fatal or life-threatening events are reported to FDA by phone or FAX within 7 calendar days. Written report should be sent to FDA within 15 calendar days for any serious unexpected adverse events for which there is a reasonable possibility that the event may have been caused by study drug(s). Any follow-up information that is significant to the report must also be sent to FDA within 15 calendar days of receipt of the new information. All filed SAEs will also be presented to the Study Monitor.

Since the trial is being conducted under a physician’s IND, **the principal investigator (listed on FDA Form 1572) overseeing the trial conduct is responsible for submitting all IND Safety Reports to the Food and Drug Administration (FDA)** in accordance with 21 CFR 312.32.

(<http://www.accessdata.fda.gov/scripts/cdrh/cfdocs/cfcfr/CFRSearch.cfm?fr=312.32>).

The FDA MedWatch 3500 Form with built-in instructions can be downloaded at:  
<http://www.fda.gov/medwatch/getforms.htm>. Click on “Mandatory Reporting” link.

Ensure that both the event intensity (mild, moderate, severe) and investigator's causality assessment (unrelated or related) are included in the description of the Adverse Event (box 5) on the FDA 3500A form.

In cases where the investigator learns of the SAE after its occurrence and resolution, the time and circumstances of the event should be recorded. The reporting requirements must still be followed.

In addition, the investigators are also responsible for timely reporting of SAEs occurring at their clinical study site to their local Institutional Review Board (IRB)/Ethics Committee (EC) and/or Central IRB (if applicable).

All adverse events occurring during the study, whether or not attributed to study drug, should be included in the investigator's annual IND report to FDA. A copy of any 7 or 15-day reports sent to FDA related to AC164594 should be sent to Amryt's Safety Department (by Fax or mail) within 24 hours of notification or discovery of the event.

The principle investigator may decide to withdraw a subject from the study due to an adverse event. Likewise, the Study Monitor may decide that a subject will need to be withdrawn. A subject may also voluntarily withdraw from treatment due to what he perceives as an intolerable adverse event. If any of these occur, the subject must undergo an end-of study assessment and be given appropriate care under medical supervision until symptoms cease or the condition becomes stable.

#### **5.5 NONSERIOUS ADVERSE EVENT DEFINITION**

A nonserious adverse event is an AE not classified as serious.

#### **5.6 NONSERIOUS ADVERSE EVENT COLLECTION AND REPORTING**

The collection of nonserious AE information should begin at initiation of study drug. Nonserious AE information should also be collected from the start of a placebo lead-in period or other observational period intended to establish a baseline status for the subjects.

Nonserious AEs should be followed to resolution or stabilization, or reported as SAEs if they become serious (see Section 1.1.1). Follow-up is also required for nonserious AEs that cause interruption or discontinuation of study drug, or those that are present at the end of study treatment as appropriate. All identified nonserious AEs must be recorded and described on the nonserious AE page of the CRF (paper or electronic).

Completion of supplemental CRFs may be requested for AEs and/or laboratory abnormalities that are reported/identified during the course of the study.

#### **5.7 SPECIAL SITUATION REPORTS**

Special situations related to the use of the study medication that are not classified as either serious adverse events or non-serious adverse events shall also be reported to the sponsor. These reports would include the following, regardless of whether or not an associated event occurred:

- Drug exposure and outcomes of use of metreleptin during pregnancy and breastfeeding, including drug exposure shortly prior to or during pregnancy or during lactation
- Lack of efficacy (including cases of incomplete, decreased or delayed drug effect)
- Suspected transmission of an infectious agent
- Overdose
- Underdose
- Off-label and misuse
- Medication errors
- Occupational exposure

#### **5.8 LABORATORY TEST ABNORMALITIES**

The following laboratory abnormalities should be captured on the non-serious AE CRF Page or SAE Report Form (paper or electronic) as appropriate:

- Any laboratory test result that is clinically significant or meets the definition of an SAE
- Any laboratory abnormality that required the subject to have the study drug discontinued or interrupted
- Any laboratory abnormality that required the subject to receive specific corrective therapy.

It is expected that wherever possible, the clinical, rather than the laboratory term would be used by the reporting investigator (e.g., anemia versus low hemoglobin value).

## **5.9 PREGNANCY**

If, following initiation of the investigational product, it is subsequently discovered that a study subject is pregnant or may have been pregnant at the time of investigational product exposure, including during at least 6 half-lives after product administration, the investigational product will be permanently discontinued in an appropriate manner (e.g., dose tapering if necessary for subject safety). Protocol-required procedures for study discontinuation and follow-up must be performed on the subject unless contraindicated by pregnancy (e.g., x-ray studies). Other appropriate pregnancy follow-up procedures should be considered if indicated.

The investigator must immediately notify the Amryt (or designee) Medical Monitor of this event and complete and forward a Pregnancy Surveillance Form to BMS (or designee) within 24 hours and in accordance with SAE reporting procedures described in Section 5.4.

Follow-up information regarding the course of the pregnancy, including perinatal and neonatal outcome and, where applicable, offspring information must be reported on the Pregnancy Surveillance Form.

If, following initiation of the investigational product, it is subsequently discovered that a study subject is pregnant or may have been pregnant at the time of investigational product exposure, including during at least 6 half-lives after product administration, the investigational product will be permanently discontinued in an appropriate manner (e.g., dose tapering if necessary for subject safety). Protocol-required procedures for study discontinuation and follow-up must be performed on the subject unless contraindicated by pregnancy (e.g., x-ray studies). Other appropriate pregnancy follow-up procedures should be considered if indicated.

The investigator must immediately notify the Amryt (or designee) Medical Monitor of this event and complete and forward a Pregnancy Surveillance Form to Amryt (or designee) within 24 hours and in accordance with SAE reporting procedures described in Section 5.4.

Follow-up information regarding the course of the pregnancy, including perinatal and neonatal outcome and, where applicable, offspring information must be reported on the Pregnancy Surveillance Form.

Any pregnancy that occurs in a female partner of a male study participant should be reported to the sponsor. Information on this pregnancy will be collected on the Pregnancy Surveillance Form.

## **5.10 OVERDOSE**

All occurrences of overdose must be reported as SAEs (see Section 5.4 for reporting details).

An overdose is defined as the accidental or intentional administration of any dose of a product that is considered both excessive and medically important. All occurrences of overdose must be reported as an SAE (see Section 6.1.1 for reporting details).

## **5.11 OTHER SAFETY CONSIDERATIONS**

Any significant worsening noted during interim or final physical examinations, electrocardiograms, x-rays, and any other potential safety assessments, whether or not these procedures are required by the protocol, should also be recorded as a nonserious or serious AE, as appropriate, and reported accordingly.

## **6. WOMEN, MINORITY AND CHILDREN INCLUSION IN CLINICAL RESEARCH**

**1. Inclusion of Women:** The use of pregnant women is not the central focus of this research. Pregnancy, women who think they may be pregnant, women who are actively trying to conceive, and women who are currently breast-feeding are exclusion criteria for enrollment in this study. The general informed consent documents will advise sexual abstinence or use of contraception for female participants of child bearing age. The use of metreleptin is intended to provide direct benefit to women participating in this trial. There are no other accepted medical treatments that are likely to provide the same benefit.

**2. Inclusion of Minorities:** In our study, all patients with physician confirmed lipodystrophy and ultrasound confirmed non-alcoholic fatty liver disease will be recruited regardless of race and ethnicity. We will continue to do every effort to recruit minorities. If the number of minorities seems to be disproportionately low, we will ask for help from the MCRU Minority Recruitment Board.

**3. Inclusion of Children:** Subjects < 5 years old will not be included in this study as they would require a pediatric expertise not available at this study location. Subjects ≥ 5 years old will be included in this study as NAFLD in lipodystrophic patients is a rare disease with no other approved option for treatment. Liver biopsies are considered to be standard of care treatment for lipodystrophic patients and therefore these juvenile patients will not be placed at an unacceptable risk by having two liver biopsies performed as part of this research study. In this protocol's parent study and **in an ongoing study, FHA101, four pediatric patients have been successfully and safely treated with metreleptin.**

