### **Exploratory outcomes:**

We will measure change in liver function tests, alanine aminotransferase (ALT) and aspartate aminotransferase (AST). We will also explore body weight, body composition, free fatty acid levels, and HOMA-IR.

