## 2.2 INCLUSION AND EXCLUSION CRITERIA

### *Inclusion criteria for initial phase of the study:*

- Previously completed study protocol:
  - CLINICAL PROTOCOL to investigate the efficacy of recombinant human leptin (METRELEPTIN) in nonalcoholic steatohepatitis (NASH) or nonalcoholic fatty liver disease (NAFLD) associated with lipodystrophy, MB002-014 (IRMBED: HUM00058708)
- Demonstrates clinical benefit as defined by meeting at least one of the following criteria upon completion of the above stated protocols:
  - Reduction of HbA1c  $\geq$  1.0% or,
  - Reduction of triglycerides  $\geq$  30% of baseline or,
  - Decrease in insulin requirements  $\geq$  40% or,
  - Reduction in total NASH score by  $\geq$  2 points,
  - Significant worsening of metabolic parameters after discontinuation of Metreleptin if discontinuation has been undertaken.
  - A health condition that appears to have significantly improved by metreleptin for which two independent health care providers make a request to prevent drug discontinuation. In addition, the PI has to document absence of contraindications for drug continuation (such as bone marrow suppression).
- Is male or female  $\geq$  5 years old at baseline.
- Is male, female not of childbearing potential, or meets all the following criteria if female of childbearing potential (including perimenopausal women who have had a menstrual period within one year):
  - Not breastfeeding
  - Negative pregnancy test result (human chorionic gonadotropin, beta subunit [ $\beta$ hCG]) at baseline (not applicable to hysterectomized females).
  - Must practice and be willing to continue to practice appropriate birth control (defined as a method which results in a low failure rate when use consistently and correctly, such as implants, injectables, oral contraceptives, some intrauterine contraceptive devices, sexual abstinence, tubal ligation, or a vasectomized partner) during the entire duration of metreleptin treatment.
- Has physician-confirmed lipodystrophy as defined by evidence of partial (limbs) loss of body fat outside the range of normal variation.
- If  $\geq$  18 years of age, is able to read, understand and sign the U of M IRBMED approved informed consent form (ICF), communicate with study physician and study team, understand and comply with protocol requirements.

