### *Study Inclusion:*

Criteria for continuation into the long-term phase is based solely on proven clinical benefit using criteria universally accepted to be beneficial. The following criteria are accepted as evidence of substantial clinical benefit upon completion of CLINICAL PROTOCOL to investigate the efficacy of recombinant human leptin (METRELEPTIN) in nonalcoholic steatohepatitis (NASH) or nonalcoholic fatty liver disease (NAFLD) associated with lipodystrophy, MB002-014 (IRMBED: HUM00058708):

- Reduction of HbA1c  $\geq$ 1.0% or,
- Reduction of triglycerides  $\geq$ 30% of baseline or,
- Decrease in insulin requirements  $\geq$ 40% or,
- Reduction in total NASH score by  $\geq$ 2 points.
- Significant worsening of metabolic parameters after discontinuation of Metreleptin if discontinuation has been undertaken.

- A health condition that appears to have significantly improved by metreleptin for which two independent health care providers make a request to prevent drug discontinuation. In addition, the PI has to document absence of contraindications for drug continuation (such as bone marrow suppression).

*Study group:* We will enroll up to a total of up to 15 subjects to receive study drug Metreleptin from our parent studies.

*Restorative leptin therapy:* This is defined as administration of recombinant methionyl-human leptin subcutaneously to achieve high normal levels of circulating leptin in individuals who started out with lower than normal or low normal levels of circulating leptin(1, 2). Recombinant human leptin will be provided by Amryt Pharma (Boston, MA). Previous experience from patients with lipodystrophy or with congenital absence of leptin indicates that this goal can be achieved by administration of 0.02 to 0.10 mg/kg/day in adult males depending on baseline leptin concentrations and body surface area of the patients. In this study, patients will be treated with 2.5 and 5 mg /day (male and female respectively) to achieve high physiological concentrations. Higher dose titrations can be used in the judgment of the PI as indicated up to 10 mg daily. It is important to note that the patients enrolling in this long term study will be on metreleptin therapy that has been found effective, therefore, their dose will likely not change during this protocol. .

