*Treatment:* Up to fifteen patients will be enrolled into this long-term treatment extension study. Patients will be continued on metreleptin treatment as mentioned. This will be injected subcutaneously after reconstitution once a day in the morning at approximately the same time of the day that fits the subject's calendar. Dose may be titrated up to 15 mg daily based on metabolic response as needed.

*Follow-up schedule and monitoring:* Scheduled outpatient visits will occur at 6 month intervals. Tolerability will be assessed at each visit. During each visit, patients', weights, BMI, injection site inspection and basic laboratory data (comprehensive metabolic panel (fasting glucose, BUN, creatinine, sodium, potassium, chloride, CO2, calcium, total protein, albumin, total bilirubin, AST, ALT, alkaline phosphatase), fasting insulin, fasting leptin levels, fasting lipid panel (total cholesterol, triglycerides, HDL, LDL)), will be recorded. Throughout the study, lab work for CBC with differential count and creatinine kinase will be obtained at each visit.

Unscheduled visits may occur at more frequently than ever six months in order to follow-up on any adverse event or unanticipated health issues participants may be having.

*Study Termination:* Patient participation will be concluded five years after the patient's baseline appointment. At this time normal follow-up study procedures will be conducted, final drug accountability will be performed and patient will be transitioned to clinical care.

*Preparation for study visits:* Subjects will be asked to refrain from alcohol or tobacco use for 72 hours prior to the visit. They will report to the Research Center after 10 hours of fasting. They will be allowed to consume water overnight prior to the studies.

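### Does Section 6's mention of two liver biopsies in children mean that an invasive procedure is missing from the plan?

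*Protocol*

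**What the plan says.** The paragraph on children in Section 6 sets the lower age limit at 5 years. It gives as the reason for inclusion that "NAFLD in lipodystrophic patients is a rare disease with no other approved option for treatment". It then turns to procedural risk, saying that "Liver biopsies are considered to be standard of care treatment for lipodystrophic patients" and, from that, that "these juvenile patients will not be placed at an unacceptable risk by having two liver biopsies performed as part of this research study". Its last sentence mentions the parent study by name, together with another ongoing study, as prior paediatric experience with the drug.

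Elsewhere the protocol describes a non-invasive extension study. For the liver, the exploratory outcomes begin "We will measure change in liver function tests, alanine aminotransferase (ALT) and aspartate aminotransferase (AST" and name no tissue measure. Section 2.2 says "Scheduled outpatient visits will occur at 6 month intervals" and lists weight, BMI, injection-site inspection and blood tests. Of the five-year closing visit it says "At this time normal follow-up study procedures will be conducted, final drug accountability will be performed". Section 2.3 covers fasting blood chemistry, HOMA-IR and stored samples for circulating markers. Section 4.1 names blood draws and the time taken by visits as the evaluation risks.

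**The concern.** Read literally, the protocol disagrees with itself on whether minors undergo an invasive procedure. The phrase is hard to read as meaning the parent study, because the next sentence names that study separately and the same paragraph uses similar wording for the current protocol.

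Two consequences would be worth correcting. If biopsies are intended, a procedure with real risk is missing from the procedures, the schedule and the stated risks. If they are not, Section 6 argues the acceptability of a procedure that this study does not perform and says nothing specific about the procedures that children will have. An ethics reviewer looking only at Section 6 could not tell which applies.

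**Working it through.** No formula applies; the check is a side-by-side reading of every place where a liver biopsy would have to appear if it were part of this study.

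| Place in the protocol | Content | Liver biopsy? |
|---|---|---|
| Section 1, primary and secondary outcomes | Fasting triglycerides; HbA1c | None |
| Section 1, exploratory outcomes | ALT, AST, weight, body composition, free fatty acids, HOMA-IR | None |
| Section 2.2, follow-up and termination | Outpatient visits with examination and blood tests; routine procedures and drug accountability at the end | None |
| Section 2.3 A and B | Fasting chemistry, HOMA-IR, stored samples | None |
| Section 4.1 | Risks of blood draws and visit burden | None |
| Appendix, Table 1 | Samples, HOMA-IR, vital signs, study drug | None |
| Section 6, paragraph on children | Risk statement | Two |

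Three further readings were tested.

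1. *Does an entry criterion imply a biopsy here?* One benefit criterion is a fall of at least 2 points in the total NASH score. Section 2.2 applies the criteria "upon completion of the above stated protocols", and the Study Inclusion text repeats this: "The following criteria are accepted as evidence of substantial clinical benefit upon completion of CLINICAL PROTOCOL". The score is therefore judged on parent-study data and requires no tissue in the extension.

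2. *Could the biopsy be covered in text not available?* Part of Section 4.2 is missing from the text reviewed, but that section concerns the risks of the drug. Section 4.1, on the risks of evaluation methods, is complete, and so are Sections 2.2 and 2.3. The only other biopsy mentioned is a generic skin-biopsy example in the SAE rules of Section 5.4.

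3. *Is leftover wording plausible?* A reduction in a score needs two readings, one before and one after treatment, which fits two biopsies in the parent study if that score was histological. The paragraph on minorities in Section 6 also describes recruitment of patients with ultrasound-confirmed fatty liver, yet Section 2.2 has no ultrasound criterion. Both points suggest that Section 6 was not fully adapted to the extension. This is an inference; the protocol does not say so.

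The last question is whether children are left without any risk statement. Section 4.1 sets no age limit. It keeps blood volume within the IRB's restrictions, describes pain and infection risk from blood draws as minimal, and addresses the burden of visits. It therefore covers the listed procedures for minors too, though without a child-specific argument.

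**The case for a change.** The strongest case for acting is that this sentence is Section 6's only argument about procedural risk to minors, and it is wrong for this study whichever way it is read. Standard-care status does not explain the omission: Section 2.3 lists its routine blood tests even though they are charged to insurance as ordinary care. Nor does calling it leftover wording excuse it, since that would confirm the sentence is inaccurate.

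Much of this stands. The sentence does not match the protocol and nothing in the text explains it away. Two parts do not carry through. First, the possibility that a biopsy was left out of the schedule has almost no support. The lists are not exhaustive (body composition is an outcome without a stated method, and Table 1 has no separate row for the blood count or creatine kinase), so absence from any one list proves little. But no outcome uses histology and all the operative sections agree. Second, it is too broad to say that the risk of the procedures performed is not stated for children, because Section 4.1 applies to every participant. What remains is an inaccurate supporting sentence in a section that instructs nobody to do anything.

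**Conclusion.** The mismatch is genuine but clerical. Two liver biopsies are stated in one justification sentence, and none is specified in the outcomes, visits, procedures, evaluation risks or schedule. Staff who follow Sections 2.2 and 2.3 and Table 1 would carry out the same procedures, collect the same safety data and reach the same conclusions with or without the sentence. Deleting it would change no sample size, outcome, visit or analysis, and the stated reason for including children does not depend on it. No change to the plan follows; reconciling the Section 6 sentence with Sections 2.2, 2.3, 4.1 and Table 1 is housekeeping for the next amendment.

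This rests on two assumptions: that site staff work from the operative sections rather than from Section 6, and that no biopsy is intended, as the agreement of those sections indicates. Only the sponsor-investigator can confirm the second. The protocol does not say how many of the up to 15 subjects, if any, would be minors.
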